Testing of Hypotheses: Statistics and Data Analysis

Specific Aim #1: Objective and subjective measures of anxiety will be positively correlated with each other. A primary analysis will examine Pearson correlations between subjective measures of anxiety (i.e., the HDRS Anxiety-Somatization Factor Scale, HAM-A, and CUDOS-A) and eye-blink startle response. Similarly, we will examine correlations between subjective anxiety and reward responsiveness. We will analyze the data to ensure that linearity exists. If linearity does not exist, we will conduct comprehensive sub-analyses to find the best way to characterize the relationship of all data. For example, we will use covariates (e.g., clinical descriptors such as treatment failures) to determine their role in creating non-linearity.

Specific Aim #2: Greater psychophysiological and cognitive objective measures of anxiety will predict better antidepressant response to ketamine, regardless of subjective depression symptoms. We will use a nonlongitudinal linear regression model to assess the extent to which the combination of pre-treatment psychophysiological (e.g., anxiety-potentiated eye-blink startle) and cognitive reward processing (high versus low reward responsiveness) predict the antidepressant treatment response to ketamine (Visits 3 and 4). Antidepressant response to ketamine will be defined as a $\geq 50\%$ improvement in HDRS scores (primary dependent outcome measure).

Specific Aim #3: In ketamine responders, psychophysiological measurements will show a significantly larger decreases in magnitude compared to ketamine nonresponders; greater improvements will be seen in cognitive reward processing measures in ketamine responders. We will use longitudinal analyses (linear mixed effects random regression models) to analyze the effect of ketamine on

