the biomarkers. These models account for the correlation of observations from the same individual. For the change in startle magnitude post-ketamine, the model will include the change in startle magnitude as the outcome, and time (Visit 2 and 4) as the predictor. For the change in reward processing post-ketamine, the model will include the change in reward processing as the outcome, and time (Visit 2 and 4) as the predictor. The coefficient for the correlations in this model quantifies the rate of change in the psychophysiological and cognitive measures associated with a change in depressive symptoms. A coefficient significantly different from zero indicates that changes in the clinical measures of depression are associated with changes in psychophysiological and/or cognitive measures. We will also perform between-group comparisons of measurements for responders vs. nonresponders. All models will be fit using SAS software, $\alpha=0.05$, two-tailed.

Sample Size Determination:

The sample size for Aims #1 and #2 was calculated using the G*Power Sample Size calculator (Version 3.9.1.2; downloaded from <http://www.gpower.hhu.de>) and was based on findings from a *post-hoc* analysis of the antidepressant treatment response to ketamine in anxious versus nonanxious depressed patients, where anxious depression predicted a better response to open-labeled ketamine.(6) The anxious depression effect size (Cohen's *d*) reached its maximum of $d=0.76$ on Day 2 post-infusion. With this, for Aims #1 and #2, we estimate requiring 58 patients with power >0.8 , $r=0.35$ and an $\alpha=0.05$, two-tailed, in order to reject the null hypothesis that there will be no correlations with baseline psychophysiological and cognitive measures between ketamine responders and nonresponders. For Aim #3, a sample size of 58 would allow us to detect a moderately-large effect size (Cohen's $d\geq 0.75$) for between-group comparisons. In order to account for potential drop-outs, we will recruit 70.

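### Aim #1's fallback when linearity fails is an unspecified, unadjusted search, so its false-positive rate is not controlled at 0.05

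*Combined protocol and SAP*

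**What the plan says.** Section VI, under Testing of Hypotheses, Specific Aim #1, opens: "A primary analysis will examine Pearson correlations between subjective measures of anxiety". The measures are given as "i.e., the HDRS Anxiety-Somatization Factor Scale, HAM-A, and CUDOS-A) and eye-blink startle response", so there are three scales and none is named as the main one. A second set follows: "Similarly, we will examine correlations between subjective anxiety and reward responsiveness".

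The linearity step is one sentence, "We will analyze the data to ensure that linearity exists", with no test, plot or threshold attached. The fallback is "If linearity does not exist, we will conduct comprehensive sub-analyses to find the best way to characterize the relationship of all data". Its only illustration is that "we will use covariates (e.g., clinical descriptors such as treatment failures) to determine their role in creating non-linearity".

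The end of the Aim #3 text adds: "All models will be fit using SAS software, $\alpha=0.05$, two-tailed". The Sample Size Determination paragraph also applies a two-tailed 0.05 to Aims #1 and #2, and sizes the study on rejecting a null hypothesis. No adjustment for multiple analyses appears in either place.

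**The concern.** The fallback is a stated rule for a primary analysis, and the rule is to let the data choose. Three things are left open: when the search starts, what it may contain, and which of its results counts as the Aim #1 finding. If the best-looking form is chosen on the same patients and then judged at 0.05, its p-value does not have its nominal meaning.

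At stake is the claim that objective and subjective anxiety are related in these patients. A reader of the final report could not tell a real link from one produced by trying several forms and covariates.

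**Working it through.** **The plan's own figure.** The documents give no false-positive rate for the fallback. Their one relevant figure is N=58 (r=0.35, power above 0.8, two-tailed 0.05). Converting d=0.76 gives r = 0.76/√(0.76² + 4) = 0.355. The noncentral-t power for a point-biserial correlation is then 0.812 at N=58. At r=0.35 exactly it is 0.799, and N=59 is needed. So 58 is reproduced closely. For a Pearson correlation of two continuous measures at r=0.35, power at 58 is about 0.78.

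**Inputs.** From the documents: n=58, two-tailed 0.05, Pearson first, search only if linearity fails. Assumed, because the documents are silent: the linearity check (a test of the quadratic term, at 0.05 or 0.20), the list of alternatives, and startle that is either normal or right-skewed. There is no true association. Any p below 0.05 among the analyses run counts as a positive.

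**Formula.** Overall rate = P(check fails) × P(some analysis rejects, given failure) + P(check passes and Pearson rejects).

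**Worked case** (normal startle, five forms, check at 0.05). The check fails in 0.053 of data sets, and some form rejects in 0.546 of those. Pearson alone rejects in 0.050. Treating the check and the Pearson test as independent: 0.053 × 0.546 + 0.947 × 0.050 = 0.029 + 0.048 = 0.077, which matches the simulated rate.

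**Results** (20,000 null data sets per distribution; ranges span normal and skewed startle):

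| Assumed alternatives | Search always run | Overall, check at 0.05 | Overall, check at 0.20 | Within the branch, check at 0.05 |
|---|---|---|---|---|
| Pearson, Spearman | 0.066–0.079 | 0.051–0.052 | 0.054–0.055 | 0.07–0.20 |
| plus quadratic | 0.093–0.105 | 0.075–0.077 | 0.081 | 0.54–0.69 |
| five forms (plus log, median split) | 0.123–0.132 | 0.075–0.077 | 0.084–0.086 | 0.55–0.69 |
| ten analyses (plus two covariate sets, an interaction, two subgroups) | 0.183–0.187 | 0.076–0.079 | 0.094–0.098 | 0.58–0.71 |

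A separate run with a different set of nine analyses (5,000 null data sets) gave 0.091–0.102 with the check at 0.05 and 0.115–0.136 at 0.20. That is the source of the upper figure of about 0.14.

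**Why the branch rate is high.** A data set enters the branch because its quadratic term is already large. A curved fit to the same data is then likely to look significant.

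**A fixed fallback.** If Spearman replaces Pearson whenever the check fails, the overall rate is 0.043–0.052 across the same settings. If either test may count, it is 0.051–0.055.

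**The case against.** The strongest reply is that the fallback is descriptive. The plan speaks of sub-analyses that characterise a relationship, and the covariates are there "to determine their role in creating non-linearity". It does not say that the best-fitting form replaces Pearson, or that forms are chosen by smallest p. A reader might infer both, and the documents do not support either as a statement of what will be done. What stands is that nothing rules it out: the passage sits under hypothesis testing, belongs to a primary analysis, and names no confirmatory result.

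A second tempting reading is that the rule inflates the error rate two- to nearly four-fold. Independent looks give that range: 1 − 0.95² = 0.0975 for two and 1 − 0.95⁴ = 0.185 for four. Running the larger assumed sets in every data set gives similar rates. But the plan searches only after linearity fails, and it lists no median split, quadratic or subgroup. With the condition applied, the overall rates are those in the conditional columns, and no multiplier is a property of the plan.

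Three further points reduce the weight. If the relationship really is non-linear, an association exists and rejecting is not a false positive; only chance non-linearity counts. The hypothesis is a positive correlation, so a curved or single-subgroup result would not strictly confirm it, although the simulations count it. And Aim #1 is a baseline correlation, not the primary clinical endpoint, in what Section IX calls a physiological biomarker study. All three are fair. They limit the size of the problem without supplying the missing rule.

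**Conclusion.** The point holds as a gap in error control. The fallback has no trigger, no list and no named confirmatory result, and the only stated error rate is an unadjusted two-tailed 0.05. The Aim #1 false-positive rate is therefore not controlled at 0.05.

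Its size cannot be derived from the documents. Under the assumptions above it runs from almost no inflation, when the only alternative is a rank correlation, to about 0.10 with ten analyses, and about 0.14 with the wider assumed set and a check at 0.20. The low end is not secured, because an informal look at a scatterplot would satisfy the plan's wording. The more serious exposure is conditional: once chance curvature has opened the branch and a curved fit is allowed, a nominally significant result is more likely than not with the check at 0.05.

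This should be changed before analysis, but it does not undermine the study design.

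**What to change.** Replace the fallback sentence with a fixed rule:

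- State the linearity criterion and the scale on which startle is analysed before looking at the data.
- Keep Pearson on that scale as the primary test.
- If the criterion fails, use Spearman as the single confirmatory result.
- Label covariate, non-linear and subgroup analyses exploratory and report them without significance claims.

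The cost is a few lines of text and two small losses. If the data are in fact bivariate normal, Spearman has power of about 0.73 against 0.78 for Pearson at n=58 and r=0.35. Spearman also does not capture non-monotone shapes, which would stay exploratory.

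This does not address the three anxiety scales each tested at 0.05. Even with linearity intact, they give an any-scale rate of about 0.08 to 0.15 for assumed inter-scale correlations from 0.9 down to 0. That is a separate multiplicity issue and needs its own rule.

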7. Acetaminophen 325mg tablets, take 1 - 2 tablets PO PRN headache, may repeat x1 after 30 min
8. Ibuprofen 200mg tablets, take 2 tablets PO PRN headache, may repeat x1 after 30 min

Research staff will be responsible for administering scales and for monitoring side effects. In order to minimize external stimuli, ketamine administration will occur in a room with low lighting and minimal noise throughout the administration, as well as during the monitoring period. Participants will be given a small snack 2 hours after the end of the ketamine infusion.

Discharge: After the ketamine infusion, if medically stable (as deemed by a board-certified physician study investigator), participants will be discharged home with a responsible family member or other adult caretaker. Discharge home will be based on criteria established by the MGH Department of Anesthesia practices for discharge from the hospital following ambulatory surgery. The participant must have stable vital signs, be able to respond appropriately to normal commands, be pain free, be free from any nausea and vomiting, and have no bleeding from the intravenous sites. Participants must be able to walk unassisted and have an accompanying adult to escort them home. Participants will be advised not to return to work and against driving or operating heavy equipment for 24 hours.

Medication Transport and Storage

The MGH Research Pharmacy and MGH CRC will store medications, including ancillary medications.

Devices to be Used

N/A

Procedures/Surgical Intervention

N/A

VI. Biostatistical Analysis

Specific Data Variables to be Collected

As described above, we will administer the following scales at all visits (Visits 1-4): HDRS, MADRS, HAM-A, CUDOS-A, YMRS, SFQ, and SHAPS.

We will administer the following at Visit 1 only (screening): M.I.N.I., ATRQ, and ETISR-SF.

We will administer the following scales during Visit 3 only (ketamine): BPRS and CADSS at baseline, +40 minutes, +80 minutes, and +120 minutes in relationship to the time of ketamine infusion.

Vital Signs will be recorded once at Visit 1 (the screening visit), and again at Visit 3 at baseline, +0 minutes, +5, +10, +15, +20, +30, +40, +60, +90, +120, +180 minutes in relationship to the time of ketamine infusion.

Study Endpoint

Primary clinical endpoint is change in the HDRS₂₈ total score. Scores that decrease by $\geq 50\%$ from baseline will be considered "response."

Specific Statistical Methods

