Expected Outcomes/Results: We expect that subjective and objective measures of anxiety will be at least moderately correlated in patients with mood dysregulation. Further, we predict that patients with higher pre-treatment levels of objective anxiety, as measured by psychophysiological and cognitive assessments, will have significantly greater antidepressant responses to ketamine, compared to patients with lower pre-treatment objective anxiety. These results will significantly contribute to the paucity of information regarding biomarkers of diagnosis and antidepressant response and provide insight into the anxiety and reward neurocircuitry that could contribute to the pathophysiology of anxious depression.

VII: Risks and Discomforts

Complications of Procedures

Safety: At any time during the study, participants, family members, and treating psychiatrist will be encouraged to contact the principal investigator via phone or pager in the case of adverse events or worsening symptoms. The treating psychiatrist will be immediately notified of any concerns.

Drug Side Effects and Toxicities

Ketamine: Ketamine is a relatively commonly used anesthetic in both veterinary and human medicine. Although it has a good safety profile overall, ketamine has documented sympathomimetic activity that may result in mild to moderate increases in heart rate, blood pressure, and cardiac output, though this activity is generally short-lived.(47) Findings from previous research on single- and repeated-dose intravenous ketamine for treating depression have provided evidence that the autonomic changes that may occur during the active administration (i.e., elevated blood pressure, pulse) return to normal shortly after the infusion stops, with no clinically significant sequelae.(48, 49) Other possible side effects reported during ketamine infusion include arrhythmia, increased salivation, increased bronchial secretions, horizontal nystagmus, euphoria and hallucinations. Nystagmus may persist for a period after the ketamine infusion has terminated.

Rare side effects are allergic reactions (skin rash), pain at site of injection, increased intraocular pressure, ulcerations and inflammation in the bladder (reported in ketamine abusers). Ketamine is a controlled substance and has the potential for abuse and dependence, in particular in participants with history of drug abuse. Participants with history of substance abuse or dependence in the previous year will be excluded.

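### Aim #2 claims prediction independent of depression symptoms, but its regression names no baseline symptom term

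*Combined protocol and SAP*

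**What the plan says.** **The hypothesis.** In section VI (Specific Statistical Methods, Specific Aim #2), greater objective anxiety "will predict better antidepressant response to ketamine, regardless of subjective depression symptoms".

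**The model.** One model follows: "We will use a nonlongitudinal linear regression model to assess the extent to which the combination of pre-treatment psychophysiological" measures, with anxiety-potentiated startle as the example, and "cognitive reward processing (high versus low reward responsiveness) predict the antidepressant treatment response to ketamine (Visits 3 and 4". No depression or anxiety scale is listed as a predictor. The only mention of covariates in the section is under Specific Aim #1, where they serve to explain departures from linearity.

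**The outcome.** Study Endpoint says "Primary clinical endpoint is change in the HDRS₂₈ total score" and then calls a fall of at least 50% a response. Aim #2 uses the same threshold ("Antidepressant response to ketamine will be defined as a" 50% or greater improvement in HDRS). Sample Size Determination states the null as "there will be no correlations with baseline psychophysiological and cognitive measures between ketamine responders and nonresponders".

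**What links symptoms to both sides.** Expected Outcomes/Results says "We expect that subjective and objective measures of anxiety will be at least moderately correlated in patients with mood dysregulation". Section II (Specific Aim #1) expects patients with anxious depression to show higher startle and lower reward responsiveness. Section I reports that anxious depression predicted a better response to ketamine. Aim #1 lists "subjective measures of anxiety (i.e., the HDRS Anxiety-Somatization Factor Scale, HAM-A, and CUDOS-A" as its anxiety scales, so one of them is a factor of the outcome scale.

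**The concern.** A coefficient supports a statement about prediction independent of symptoms only if symptoms are held fixed when it is estimated. Here they are not. The protocol itself describes the confounding path: anxious symptoms go with the biomarkers, and anxious symptoms go with response. A startle measure that added nothing to a rating scale would still tend to correlate with outcome.

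This matters because section I motivates the objective measures by noting that a symptom-based diagnosis already appears to predict response. The open question is whether a biomarker adds to that. A positive result from the model as written could not be told apart from the association already reported.

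The second, smaller matter is that the dependent variable is not fixed. It may be HDRS28 change or yes/no response. Linear regression is named beside a yes/no definition, and a non-longitudinal model is given two outcome visits with neither marked as primary. Several analyses fit that text, and the choice could be made after the data are seen.

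**Working it through.** **1. The plan's own figure.** Sample Size Determination gives 58 patients, r = 0.35, power above 0.8, two-sided 0.05, from d = 0.76. The source comparison had 15 and 11 patients (section I):

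r = d / √(d² + N²/(n₁n₂)) = 0.76 / √(0.5776 + 676/165) = 0.76 / 2.162 = 0.35.

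For a single predictor, the noncentral t test has df = 56 and noncentrality √58 × 0.35 / √(1 − 0.1225) = 2.85. Power is 0.7985 at 58 and 0.8055 at 59. A two-group contrast with d = 0.76 and 29 per group has power 0.81. So 58 reproduces, for one unadjusted association.

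**2. How often would a purely symptom-driven startle measure look predictive?** Assumptions, not in the documents: 58 patients; biomarker-symptom correlation a = 0.35 or 0.50; symptom-outcome correlation b = 0.10, 0.20 or 0.35; a normal underlying outcome; response rate p of 25 to 50%. If startle relates to outcome only through symptoms, its marginal correlation is a × b. For a yes/no outcome this is multiplied by φ(t)/√(p(1 − p)), with t the normal cut-point for response rate p: 0.798 at 50% and 0.734 at 25%. The test in step 1 then gives:

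| b | a | a × b | Called predictive, continuous | Called predictive, yes/no (25% to 50% response) |
|---|---|---|---|---|
| 0.10 | 0.35 | 0.035 | 5.8% | 5.4 to 5.5% |
| 0.10 | 0.50 | 0.050 | 6.6% | 5.9 to 6.0% |
| 0.20 | 0.35 | 0.070 | 8.2% | 6.7 to 7.0% |
| 0.20 | 0.50 | 0.100 | 11.7% | 8.5 to 9.2% |
| 0.35 | 0.35 | 0.1225 | 15.2% | 10.4 to 11.4% |
| 0.35 | 0.50 | 0.175 | 26.5% | 16.3 to 18.4% |

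Simulation with at least 20,000 replicates per setting agrees within one percentage point (about 26% and 18% at the top). With the correct symptom score in the model, the rate is 5% throughout.

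**3. Is HDRS28 alone enough?** Suppose the confounder is anxiety, with b = 0.35 and a correlation of 0.3 to 0.7 between anxiety and HDRS28. Adjusting a continuous outcome for HDRS28 only leaves about 8 to 23% in simulation. Adding HAM-A brings it to 5%.

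**4. What adjustment costs in power.** Suppose both biomarkers and the symptom score each correlate 0.35 with a continuous outcome, and the biomarkers correlate a² with each other.
- Unadjusted R² = 2 × 0.35² / (1 + a²) = 0.218 (a = 0.35) or 0.196 (a = 0.50).
- R² added beyond symptoms = 2 × (0.35 − 0.35a)² / (1 − a²) = 0.118 or 0.082.
- Simulated power of the joint two-biomarker test at 58: unadjusted 0.93 or 0.90; adjusted 0.72 or 0.54.

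**5. Endpoint identity.** With Visit 2 HDRS28 among the predictors, replacing Visit 4 HDRS28 by Visit 4 minus Visit 2 changes only the coefficient of Visit 2 HDRS28, by exactly 1. The biomarker coefficients are the same, so the adjusted model still analyses the named primary endpoint.

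**The case against.** **The clause is brief and nothing forbids adjustment.** It appears once, in a hypothesis line; Specific Aim #2 in section II and Expected Outcomes/Results omit it. That stands, and it makes deleting the clause a legitimate repair. It does not rescue the claim while the clause remains, because the analysis section names no symptom term. Percent improvement scales the outcome to baseline HDRS, which is not the same as conditioning on it.

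**The clause speaks of depression, while the confounding path runs mainly through anxiety.** This also stands. Aim #1 hopes the biomarkers track subjective anxiety, so conditioning on HAM-A could remove part of what they are meant to measure. HAM-A therefore belongs in a sensitivity analysis and not in the primary model.

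**The size depends on a generous correlation.** Correct. The d of 0.76 is described as the maximum, at Day 2, from a post hoc analysis, and section I defines response there by MADRS. At b = 0.10 to 0.20 the inflation is modest, which is why the table covers that range.

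**Stronger readings to avoid.** A reader might infer that the endpoint section and Aim #2 contradict each other. They do not: both use the 50% threshold, and response is derived from the HDRS. Only the form of the dependent variable and the visit are open. A reader might also infer that 58 is miscalculated, but step 1 reproduces it. Nor does the high-versus-low wording establish that reward will be dichotomised; it may give direction only, and section V (Cognitive Testing) defines continuous scores.

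**Conclusion.** The concern holds in this form: the Aim #2 model as written cannot support a conclusion of prediction independent of depression symptoms. That follows from the text and needs no assumed numbers.

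Its practical size is uncertain. Under the assumptions in step 2, the chance of a misleading positive result runs from barely above the nominal 5% to about 26% (continuous) or 18% (yes/no). The upper end requires a symptom-outcome correlation as large as the post hoc maximum.

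The unsettled outcome form and visit are a lesser point of specification. The documents give no ground for calling the enrolment target wrong, and no larger enrolment is proposed here. The change should be made, because Aim #2 is the predictive aim and the remedy uses data already planned.

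**What to change.** - **Primary Aim #2 model.** Regress Visit 4 HDRS28 total on the Visit 2 biomarkers with Visit 2 HDRS28 total as a covariate, and test the biomarker terms conditional on it. This fits the linear model named, keeps HDRS28 change as the endpoint and names Visit 4 as primary. If the team does not want to adjust, delete the independence clause.
- **Alongside.** Report 50% response by logistic or Firth regression. Report the unadjusted model too, labelled as not addressing independence from symptoms.
- **Sensitivity analysis.** Add Visit 2 HAM-A, since HDRS28 alone may not remove confounding through anxiety.
- **Sample Size Determination.** State that 58 refers to an unadjusted association.

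**Cost.** This is a change of wording in the analysis section only. HDRS and HAM-A are already rated at every visit, so no data or visits are added. The real price is power. Where symptoms overlap with the biomarkers, the adjusted test is weaker (0.72 or 0.54 against 0.93 or 0.90 in the example in step 4), because it tests the stricter hypothesis that the protocol states. The plan should say so, so that a null adjusted result is not over-read.

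### Aim #2 names a linear regression for an outcome defined as yes/no response, while the primary endpoint is continuous HDRS-28 change; settle the outcome and analyse the continuous score

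*Combined protocol and SAP*

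**What the plan says.** Section VI, Specific Statistical Methods, Specific Aim #2 gives the model: "We will use a nonlongitudinal linear regression model to assess the extent to which the combination of pre-treatment psychophysiological" and reward-processing measures predicts benefit. The outcome is taken from two visits: "predict the antidepressant treatment response to ketamine (Visits 3 and 4". The next sentence begins "Antidepressant response to ketamine will be defined as a", sets the threshold at 50% or more, and continues "improvement in HDRS scores (primary dependent outcome measure". No logistic or other binary-outcome model is named anywhere in the document.

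The Study Endpoint paragraph of the same section says "Primary clinical endpoint is change in the HDRS"-28 total score. It then separately labels a fall of at least 50% as response. The continuous score is available, because under Specific Data Variables to be Collected "we will administer the following scales at all visits (Visits 1-4): HDRS, MADRS, HAM-A, CUDOS-A, YMRS, SFQ, and SHAPS".

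Sample Size Determination sizes Aims #1 and #2 at 58 patients (r=0.35, power above 0.8, alpha 0.05 two-tailed). It starts from Cohen's d=0.76 and words the null hypothesis in terms of ketamine responders and nonresponders.

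**The concern.** Two analysts could follow Section VI faithfully and run different Aim #2 analyses. One would regress continuous HDRS-28 change on the biomarkers; the other would regress a 0/1 response indicator on them. The second pairs a linear model with an outcome that has unequal error variance and is bounded at 0 and 1.

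The binary version also reduces a 28-item score to one bit per patient. Improvements of 5% and 49% count alike, as do 51% and 95%. In a single-arm study of 58 patients, that lowers the chance of detecting a real association between biomarker and benefit, although the score is already collected and the named model already suits it.

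**Working it through.** **Inputs.** From the document: N=58, r=0.35, d=0.76, alpha 0.05 two-tailed, power above 0.8, outcome cut at 50% improvement. Assumed: response rates of 30%, 40% and 50%; bivariate normality of biomarker and HDRS improvement; one continuous biomarker.

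**Step 1: the planned sample size.**
- Converting d to r with equal groups: r = d/√(d²+4) = 0.76/√(0.5776+4) = 0.355, in line with the stated 0.35.
- Power for a two-group (point-biserial) correlation uses a noncentral t with N−2 degrees of freedom and noncentrality √(N·r²/(1−r²)). Here this is √(58×0.1225/0.8775) = 2.85, so power is 0.799; reaching 0.80 needs N=59.
- A two-sample t-test with d=0.76 and 29 per group has power 0.812.
- The bivariate-normal calculation fits less well. It needs 61 patients by simulation or 62 by Fisher z, with power at 58 of about 0.78 or 0.77.

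So 58 reproduces on the two-group reading.

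**Step 2: what the cut costs.** Cutting a normal outcome so that a proportion p responds multiplies the correlation by k = φ(z_p)/√(p(1−p)), where φ is the standard normal density. The share of r² kept is k². For p=0.5, k = 0.399/0.5 = 0.798 and k² = 0.64.

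**Step 3: power at N=58 under two readings of r=0.35.**
- Reading A: 0.35 is the responder/nonresponder correlation. The implied correlation with the score is 0.35/k.
- Reading B: 0.35 is the correlation with the score. After the cut it becomes 0.35×k.

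| Response rate (assumed) | k | k² | A: r on score | A: power on score (Fisher z to noncentral t) | B: r after cut | B: power after cut (simulated) |
|---|---|---|---|---|---|---|
| 50% | 0.798 | 0.64 | 0.439 | 0.937–0.955 | 0.279 | 0.58 |
| 40% | 0.789 | 0.62 | 0.444 | 0.943–0.960 | 0.276 | 0.57 |
| 30% | 0.759 | 0.58 | 0.461 | 0.959–0.973 | 0.266 | 0.53 |

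Under A, power on the cut outcome is the planned 0.80. Under B, power on the score is 0.78, and restoring 80% power on the cut outcome would take 95, 98 or 106 patients at 50%, 40% or 30% response (noncentral t). Rates of 60% and 70% mirror 40% and 30%. At 20%, k is 0.70 and power under B is about 0.47.

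**Step 4: does the model type matter by itself?** In 6,000 simulated trials per scenario:
- With no association, the linear model on the 0/1 outcome rejected in 4.8% (50% response) and 5.0% (30% response) of trials.
- Under Reading B, power was 0.57 for the linear model and 0.59 for the logistic likelihood-ratio test at 50% response. At 30% it was 0.52 and 0.54.
- Under Reading B, the linear model gave at least one fitted probability outside 0–1 in 22% (50% response) and 44% (30% response) of trials.

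The mismatch therefore affects predicted probabilities more than the association test.

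**The case against.** The strongest reply is that continuous change was intended all along. The Psychometric Assessments text attaches the primary-outcome label to the HDRS itself, the Aim #2 sentence puts the same label beside HDRS scores, and the Study Endpoint paragraph separates change from response. On that view the 50% threshold is only a descriptive label and the linear model is right. This is plausible, and it is why the point is a mismatch in the wording rather than a proven wrong analysis. It does not remove the need for a change: the Aim #2 outcome sentence is a threshold definition, and the sample-size null is framed around responders and nonresponders.

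Three stronger inferences are tempting but not supported:
- **That the Aim #2 test is invalid.** Type I error stays near 5%, as shown above.
- **That the trial is underpowered at 0.53–0.58.** That needs Reading B. The null wording and the fit of 58 to a two-group calculation favour Reading A, where planned power holds and the cost is a forgone gain. Reading A is not certain, since the source effect compares anxious with nonanxious patients.
- **That the trial's main question is at risk.** Sections II and VI list three aims without ranking them.

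It is also fair to say that a response rate is easier to communicate than a slope in HDRS points. That argues for keeping response as a secondary outcome.

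**Conclusion.** The point holds in a limited form. As written, the Aim #2 model and outcome do not match, and the Study Endpoint, Specific Aim #2 and Sample Size Determination paragraphs do not settle which outcome is meant. The sample size of 58 is not in dispute.

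If the yes/no outcome is used, about 36–42% of r² is given up at response rates of 30–50%. On the better-supported reading of r=0.35, this means accepting power of about 0.80 where about 0.94–0.97 was available. On the other reading, power falls from about 0.78 to 0.53–0.58.

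These figures rest on assumed response rates, bivariate normality and a single continuous biomarker. The plan combines startle with "cognitive reward processing (high versus low reward responsiveness"), so they are not the power of the planned model, and the effect of baseline adjustment was not calculated. The direction should hold wherever the relation is roughly linear, which the plan's own model presumes.

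**What to change.** In Specific Aim #2:
1. Make the outcome the continuous post-infusion HDRS-28 total score at one named visit, since a nonlongitudinal model cannot use both Visits 3 and 4 without a rule for combining them.
2. Fit it with the linear regression already named, with baseline HDRS-28 as a covariate. The Research Design Summary describes Visit 2 as the baseline assessment; the analysis text should name the visit.
3. Report response (at least 50% improvement) as a secondary outcome, analysed by logistic regression.
4. Reconcile the Study Endpoint, Specific Aim #2 and Sample Size Determination wording, including whether r=0.35 refers to the score or to responders versus nonresponders.

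Changing only to logistic regression would tidy the model but recover almost none of the lost power.

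The cost is a few sentences before analysis and no new data. The small downside is that the main Aim #2 result is in HDRS points rather than response probability; the secondary analysis keeps the latter.
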